Clinical Study Protocol

Drug Substance AZD9291 (Osimertinib)

Study Code ESR-16-12348

Edition Number 1

Date 19 Jan, 2017

Phase II study of osimertinib in NSCLC patients with EGFR exon 20 insertion mutation

Sponsor: [name], Seoul National University Hospital, Seoul, Korea

The following Amendment(s) and Administrative Changes have been made to this protocol since the date of preparation:

PROTOCOL SYNOPSIS

Phase II study of osimertinib in NSCLC patients with EGFR exon 20 insertion mutation

National Co-ordinating Investigator

[name], Associate Professor

Department of Internal Medicine

Seoul National University Hospital

[name]

Study site(s) and number of subjects planned

This study will be conducted at approximately 10 sites in South Korea with approximately 30 patients enrolled and dosed and at least 27 evaluable patients required (evaluable for the primary analysis). All patients will be recruited from South Korea.

Study period	Phase of development
Estimated date of first subject enrolled	Q2 2017
Estimated date of last subject completed	Q2 2019

Study design

This is a single-arm, non-randomized multicentre phase 2 study in NSCLC patients with EGFR exon 20 insertion mutation, whose disease has progressed on standard chemotherapy. Patients will have bi-weekly clinic visits for the first 4 weeks (1st cycle); thereafter visits will be every 4 weeks. Safety and efficacy assessments will be collected. Patients' medical care will be performed according to local clinical practice.

Objectives

Primary Objective Outcome Measure

To determine the efficacy of osimertinib in patients with advanced or metastatic NSCLC with EGFR exon 20 insertion mutation who show disease progression on standard chemotherapy.
Investigator-assessed objective response as defined by RECIST version 1.1

Secondary Objectives Outcome Measure

To evaluate the safety and tolerability of osimertinib AEs/SAEs as defined by NCI CTCAE version 4.0

To evaluate progression-free survival (PFS) PFS as defined by RECIST version 1.1

To evaluate overall survival (OS)

To evaluate the efficacy based on subtypes of EGFR exon 20 insertion mutation

To evaluate PFS based on subtypes of EGFR exon 20 insertion mutation

Target subject population

Adult patients at age \geq 19 years with locally advanced (stage IIIB) or metastatic (stage IV) NSCLC with confirmed EGFR exon 20 insertion mutation, who have received prior standard chemotherapy.

Duration of treatment

Patients may continue to receive osimertinib as long as they continue to show clinical benefits, as judged by the investigator, and in the absence of discontinuation criteria.

Investigational product, dosage and mode of administration

Osimertinib is an oral, potent, selective, irreversible inhibitor of both EGFR tyrosine kinase inhibitor (TKI)-sensitizing and -resistant mutations in NSCLC with a significant selectivity margin over wild-type EGFR. Osimertinib at 80mg dose will be administered orally once daily.

Statistical methods

The primary endpoint of this study is to evaluate the proportion of patients who achieved an objective response as assessed by the investigator according to RECIST version 1.1. Up to 30 patients will be enrolled and dosed in order to obtain at least 27 evaluable patients according to Simon's minimax two-stage design as follows: objective response, $P_0=0.05$ and $P_1=0.20$; type 1 error 5%, power 80%, and confidence limit 95%; stage 1 (objective response $\geq 1/13$) plus stage 2 (objective response $\geq 4/27$). All data will be presented for the overall full analysis set, and also by cohorts defined by subtypes of EGFR exon 20 insertion mutations (C-helix vs. loop following C-helix). Descriptive statistics will be used for all variables, as appropriate. Continuous variables will be summarised by the number of observations, mean, standard deviation, median, minimum, and maximum. Categorical variables will be summarised by frequency counts and percentages for each category. OS and PFS will be summarized using Kaplan-Meier estimates of the median event time and quartiles together with their 95% confidence intervals.

TABLE OF CONTENTS	PAGE
PROTOCOL SYNOPSIS	2
TABLE OF CONTENTS	5
LIST OF ABBREVIATIONS AND DEFINITION OF TERMS	9
1. INTRODUCTION	11
1.1 Background and rationale for conducting this study	11
1.2 Rationale for study design, doses and control groups	12
1.3 Benefit/risk and ethical assessment	13
1.4 Study Design	13
2. STUDY OBJECTIVES	15
2.1 Primary objective	15
2.2 Secondary objectives	15
2.3 Exploratory objectives	15
3. SUBJECT SELECTION, ENROLMENT, DISCONTINUATION AND WITHDRAWAL	15

3.1 Inclusion criteria	15
3.2 Exclusion criteria	16
3.3 Subject enrolment	18

PD	Progression of disease
PK	Pharmacokinetics
PR	Partial response
PRO	Patient Reported Outcomes
QT	ECG interval measured from the onset of the QRS complex to the end of the T wave
QTc	QT interval corrected for heart rate

RAC	Accumulation ratio
RBC	Red blood count
RECIST	Response Evaluation Criteria in Solid Tumours
RNA	Ribonucleic acid
SAE	Serious adverse event
SD	Stable disease
SRC	Safety Review Committee
TL	Target lesion
TKI	Tyrosine kinase inhibitor
ULN	Upper limit of normal
WBDC	Web Based Data Capture
WHO	World Health Organisation

1. Introduction

1.1 Background and rationale for conducting this study

EGFR exon 20 insertion mutations are typically located after the C-helix of the tyrosine kinase domain of EGFR1 and account for up to 4% of all EGFR mutations.² EGFR exon 20 insertion-mutant NSCLC cells are generally resistant to 1st-generation EGFR TKIs (gefitinib, erlotinib) as well as 2nd-generation EGFR TKIs (neratinib, afatinib, and dacomitinib). Clinically, overall response rates were 0% and 8.7% for NSCLC patients with EGFR exon 20 insertion mutation who received gefitinib/erlotinib³ and afatinib,⁴ respectively.

AZD9291 is an oral, potent, irreversible EGFR-TKI selective for sensitizing EGFR and EGFR^{T790M} resistance mutations with a significant selectivity margin against wild-type EGFR. As a result, AZD9291 can effectively block EGFR signaling both in EGFR single mutant cells with activating EGFR mutations and in double mutant cells bearing the resistance EGFR^{T790M} mutation. AZD9291 is currently under investigation as a treatment option in: 1) Patients with advanced EGFR^{T790M}-positive NSCLC who have previously failed an EGFR-TKI; 2) Patients with advanced EGFR-mutant NSCLC who are treatment naïve; 3) In combination with novel agents for patients with EGFR-TKI-

resistant NSCLC.

In the phase 1 dose escalation study of AZD9291 (D5160C00001, AURA1), no dose-limiting toxicities were reported in any of the dose escalation cohorts (20, 40, 80, 160, and 240mg) and a non-tolerated dose has not been defined. Based on the totality of the safety, pharmacokinetic and preliminary efficacy data, 80 mg once daily was selected as the recommended phase II dose.⁵ Data from the ongoing phase I AURA study (D5160C00001) in patients with EGFR T790M-positive NSCLC who were previously treated with EGFR TKI, have achieved promising efficacy with AZD9291; 61% (95% CI, 52-70%) of subjects achieved a response, 95% (95% CI, 90-98%) achieved disease control, medium duration of response of 12.4 months (95% CI, 8.3-not reach) and median PFS based on 38% maturity of data was 13.5 months (95% CI, 8.3-not reach), as assessed by blinded independent central review. Confirmatory phase 2 study of AZD9291 (AURA2) revealed 70% (95% CI, 64-77%) of patients achieved objective response in patients with EGFR T790M-positive NSCLC.⁶ In addition, AZD9291 had significantly greater efficacy than platinum-doublet chemotherapy in patients with EGFR T790M-positive NSCLC (AURA3).⁷ Promising evidence of efficacy has also observed in patients with treatment-naïve EGFR-mutant NSCLC treated with AZD9291 as first line EGFR TKI.⁸

Although disease progression was observed in one NSCLC patient with EGFR exon 20 insertion mutation who received AZD9291 40mg once daily,⁵ its efficacy had not been well studied in a homogenous patient population with EGFR exon 20 insertion mutation. In addition, although in vitro efficacy of AZD9291 against EGFR exon 20 insertion mutation (H773_V774HVdup) was initially disappointing,⁹ AZD9291 was potent with a wide therapeutic window in Ba/F3 cells with EGFR exon 20 insertion mutations: IC₅₀, 44-333 nM for A763_Y764insFQEA, Y764_V765insHH, A767_V769dupASV, and D770_N771insNPG in one study¹⁰; IC₅₀, 3.6-128.2 nM for A763_Y764insFQEA, V769_D770insASV, D770_N771insNPG, D770_N771insSVD, P772_H773insPR, H773_V774insNPH, H773_V774insH, and H773_V774insAH (unpublished data). Therefore, this study will be performed to investigate the efficacy of AZD9291 in NSCLC patients with EGFR exon 20 insertion mutation.

Clinical experience with AZD9291 is described in the current version of the AZD9291 IB.

1.2 Rationale for study design, doses and control groups

This open-label, single-arm, non-randomized phase 2 study has been designed to evaluate the efficacy of AZD9291 80mg once daily in NSCLC patients with EGFR exon 20 insertion mutation who

failed to standard chemotherapy.

In the phase 1 dose escalation study of AZD9291 (D5160C00001, AURA1), once daily doses of 20, 40, 80, 160, and 240mg of AZD9291 were evaluated.⁵ Based on the totality of the safety, pharmacokinetic and preliminary efficacy data, 80 mg once daily was selected as the recommended phase II dose. Please refer to the AZD9291 IB for additional details. No dosage adjustment is required due to patient age, body weight, gender, ethnicity and smoking status.

1.3 Benefit/risk and ethical assessment

This study is designed to assess the primary objective for AZD9291 efficacy while minimizing the number of patients exposed to AZD9291 based on Simon's minimax two-stage design. Pre-clinical and emerging clinical tolerability data from patients indicate that AZD9291 is generally well tolerated by patients with advanced cancer. At least 1,258 subjects have been exposed to study treatment (AZD9291 alone or AZD9291 in combination with another treatment) in the ongoing osimertinib clinical programme (excluding healthy volunteers who only received single doses of osimertinib, and excluding patients treated with osimertinib in the ongoing Studies D5160C00003, D5160C00007 and D5165C00001). The safety data from AURA extension and AURA2, supported by consistent data from AURA Phase I, indicate that osimertinib 80 mg has an acceptable safety and tolerability profile in terms of the type, frequency and severity of events, for use in patients with NSCLC.^{5,6} The most common AEs reported with osimertinib were consistent across AURA extension and AURA2 and in line with the expected profile of an EGFR TKI. AEs of decreased appetite, fatigue, and nausea occurred at an incidence of >10%, but were mostly mild in nature and non-serious. These non-specific AEs represent a range of symptoms related to NSCLC and its treatment and were reported frequently in the past medical history of this patient population (decreased appetite [12.9-16.9%], fatigue [15.7-18.4 %], nausea [6.7-9.0%]). Across all cohorts and dose levels, there were 12 patients who died due to an AE; the most frequently reported AE that led to death was pneumonia (6 patients). No other AE that led to death was reported in more than 1 patient. Taken together, AZD9291 is well tolerated and active in patients with EGFR T790M-positive NSCLC, suggesting that clinical benefits exceed the risk.

[figure not shown]
However, there has been no approved targeted agent for NSCLC patients with EGFR exon 20 insertion mutation who show disease progression on standard chemotherapy (platinum doublet

chemotherapy, etc). Based on the totality of the safety and pharmacokinetic data as well as in vitro efficacy data, AZD9291 80mg once daily might be safe and beneficial in patients with NSCLC with EGFR exon 20 insertion mutation. Please refer to the AZD9291 IB for details.

1.4 Study Design

This is a single-arm, non-randomized multicentre phase 2 study in NSCLC patients with EGFR exon 20 insertion mutation, whose disease has progressed on standard chemotherapy. Full details of the assessments conducted at each visits are shown in Table 1.

Figure 1 Study flow chart

(a) Patients will continue to receive osimertinib until objective disease progression (according to RECIST 1.1) or for as long as they are receiving clinical benefit in the opinion of the Investigator unless any of the criteria for treatment discontinuation are met first. Patients who discontinue study treatment for reasons other than disease progression must continue tumour assessments as per the protocol schedule until progression.

2. Study objectives

2.1 Primary objective

Primary Objective Outcome Measure

To determine the efficacy of osimertinib in patients with advanced or metastatic NSCLC with EGFR exon 20 insertion mutation who show disease progression on standard chemotherapy.

Investigator-assessed objective response as defined by RECIST version 1.1

2.2 Secondary objectives

Secondary Objectives Outcome Measure

To evaluate the safety and tolerability of osimertinib AEs/SAEs as defined by NCI CTCAE version 4.0

To evaluate progression-free survival (PFS) PFS as defined by RECIST version 1.1

To evaluate overall survival (OS)

To evaluate the efficacy based on subtypes of EGFR exon 20 insertion mutation

To evaluate PFS based on subtypes of EGFR exon 20 insertion mutation

2.3 Exploratory objectives

Exploratory Objective Outcome Measure

To collect and store archival tumour tissues and cell-free DNA (cfDNA) for evaluation of mutant subtypes and disease monitoring Objective response based on genetic subtypes of EGFR exon 20 insertion mutation

3. SUBJECT SELECTION, ENROLMENT, DISCONTINUATION AND WITHDRAWAL

Each subject should meet all of the inclusion criteria and none of the exclusion criteria for this study. Under no circumstances can there be exceptions to this rule.

3.1 Inclusion criteria

For inclusion in the study subjects should fulfil the following criteria:

1. Provision of informed consent prior to any study specific procedures
2. Male or female must be > 19 years of age.
3. Locally advanced or metastatic NSCLC, not amenable to curative surgery or radiotherapy with local confirmation of the presence of the EGFR exon 20 insertion mutation
4. Disease progression while on standard chemotherapy (platinum doublet chemotherapy or single-agent chemotherapy in selected patients)
5. Eastern Cooperative Oncology Group (ECOG) performance status 0-2.
6. Patients must have a life expectancy \geq 12 weeks
7. Females should be using adequate contraceptive measures, should not be breast feeding and must have a negative pregnancy test prior to start of dosing if of child-bearing potential or

must have evidence of non-child-bearing potential by fulfilling one of the following criteria at screening:

- Post-menopausal defined as aged more than 50 years and amenorrheic for at least 12 months following cessation of all exogenous hormonal treatments
- Women under 50 years old would be consider postmenopausal if they have been amenorrheic for 12 months or more following cessation of exogenous hormonal treatments and with LH and FSH levels in the post-menopausal range for the institution
- Documentation of irreversible surgical sterilisation by hysterectomy, bilateral oophorectomy or bilateral salpingectomy but not tubal ligation

8. Male patients should be willing to use barrier contraception (see Restrictions, Section0).
9. Patient is willing and able to comply with the protocol for the duration of the study including undergoing treatment and scheduled visits and examinations including follow up.
10. At least one lesion, not previously irradiated, that can be accurately measured at baseline as ≥ 10 mm in the longest diameter (except lymph nodes which must have short axis ≥ 15 mm) with computed tomography (CT) or magnetic resonance imaging (MRI) and which is suitable for accurate repeated measurements.
11. Provision of archival FFPE tissue (3 slices of 10 μ m thickness in EP tube)
12. Provision of informed consent for translational genetic research

3.2 Exclusion criteria

Subjects should not enter the study if any of the following exclusion criteria are fulfilled:

1. Involvement in the planning and/or conduct of the study (applies to both sponsor staff and/or staff at the study site)
2. Previous treatment with osimertinib
3. Treatment with an investigational drug within five half-lives of the compound
4. Patients currently receiving (or unable to stop use prior to receiving the first dose of study treatment) medications or herbal supplements known to be potent inhibitors of CYP3A4 (at least 1 week prior) and potent inducers of CYP3A4 (at least 3 week prior) (Appendix A). All patients must try to avoid concomitant use of any medications, herbal supplements and/or ingestion of foods with known inducer/inhibitory effects on CYP3A4.
5. Any unresolved toxicities from prior therapy greater than Common Terminology Criteria for

Adverse Events (CTCAE) grade 1 at the time of starting study treatment with the exception of alopecia and grade 2, prior platinum-therapy related neuropathy.

6. Any evidence of severe or uncontrolled systemic diseases, including uncontrolled hypertension and active bleeding diatheses, which in the investigator's opinion makes it undesirable for the patient to participate in the trial or which would jeopardise compliance with the protocol, or active infection including hepatitis B, hepatitis C and human immunodeficiency virus (HIV). Screening for chronic conditions is not required.

7. Patients with symptomatic CNS metastases who are neurologically unstable; however, those with asymptomatic CNS metastases who do not require steroids for at least 4 weeks prior to start of osimertinib are eligible.

8. Past medical history of ILD, drug-induced ILD, radiation pneumonitis requiring steroid treatment, or any evidence of clinically active ILD

9. Inadequate bone marrow reserve or organ function as demonstrated by any of the following laboratory values:

Absolute neutrophil count <1.5 x 10⁹/L

Platelet count <100 x 10⁹/L

Haemoglobin <90 g/L

Alanine aminotransferase >2.5 times the upper limit of normal (ULN) if no demonstrable liver metastases or >5 times ULN in the presence of liver metastases

Aspartate aminotransferase >2.5 times ULN if no demonstrable liver metastases or >5 times ULN in the presence of liver metastases

Total bilirubin >1.5 times ULN if no liver metastases or >3 times ULN in the presence of documented Gilbert's Syndrome (unconjugated hyperbilirubinaemia) or liver metastases

Creatinine >1.5 times ULN concurrent with creatinine clearance <50 ml/min (measured or calculated by Cockcroft and Gault equation); confirmation of creatinine clearance is only required when creatinine is >1.5 times ULN.

10. Any of the following cardiac criteria:

Mean resting corrected QT interval (QTc using Fredericia's formula) > 470 msec

Any clinically important abnormalities in rhythm, conduction or morphology of resting ECG (e.g., complete left bundle branch block, third degree heart block, second degree heart block)

Any factors that increase the risk of QTc prolongation or risk of arrhythmic events such as heart failure, hypokalemia, congenital long QT syndrome, family history of long QT syndrome or unexplained sudden death under 40 years of age in first degree relatives or any concomitant medication known to prolong the QT interval

11. Refractory nausea and vomiting, chronic gastrointestinal diseases, inability to swallow the formulated product or previous significant bowel resection that would preclude adequate absorption of AZD9291

12. History of hypersensitivity to AZD9291 (or drugs with a similar chemical structure or class to AZD9291) or any excipients of these agents

13. Males and females of reproductive potential who are not using an effective method of birth control and females who are pregnant or breastfeeding or have a positive (urine or serum) pregnancy test prior to study entry

14. Judgment by the Investigator that the patient should not participate in the study if the patient is unlikely to comply with study procedures, restrictions and requirements

15. Previous allogeneic bone marrow transplant.

16. Non-leukocyte depleted whole blood transfusion within 120 days of the date of the genetic sample collection.

3.3 Subject enrolment

Investigator(s) should keep a record, the subject screening log, of subjects who entered pre-study screening.

The Investigator(s) will:

1. Obtain signed informed consent from the potential subject before any study specific procedures are performed.
2. Assign potential subject a unique enrolment number.
3. Determine subject eligibility. See Sections 0.1 and 3.2.

If a subject withdraws from participation in the study, then his/her enrolment code cannot be reused.

3.4 Procedures for handling incorrectly enrolled or randomized subjects

Subjects who fail to meet the eligibility criteria should not, under any circumstances, be enrolled or receive study medication. There can be no exceptions to this rule. Subjects who are enrolled, but subsequently found not to meet all the eligibility criteria must not be randomized or initiated on

treatment, and must be withdrawn from the study.

Where a subject does not meet all the eligibility criteria but is randomized in error, or incorrectly started on treatment, the Investigator should inform the sponsor immediately, and a discussion should occur between the sponsor and the investigator regarding whether to continue or discontinue the patient from treatment. The sponsor must ensure all decisions are appropriately documented.

3.5 Methods for assigning treatment groups (Not applicable)

3.6 Methods for ensuring blinding (Not applicable)

3.7 Methods for unblinding (Not applicable)

3.8 Restrictions

The following restrictions apply while the patient is receiving AZD9291 and for the specified times before and after:

1. Females of child-bearing potential should use reliable methods of contraception from the time of screening until 3 months after discontinuing AZD9291. Acceptable methods of contraception include total and true sexual abstinence, tubal ligation, hormonal contraceptives that are not prone to drug-drug interactions (IUS Levonorgestrel Intra Uterine System [Mirena], Medroxyprogesterone injections [Depo-Provera]), copper-banded intra-uterine devices, and vasectomized partner. All hormonal methods of contraception should be used in combination with the use of a condom by their male sexual partner for intercourse.

2. Male patients should be asked to use barrier contraceptives (i.e., by use of condoms) during sex with all of their female partners during the trial and for a washout period of 3 months. Patients should not father a child for 6 months after completion of AZD9291 treatment. Patients should refrain from donating sperm from the start of dosing until 6 months after discontinuing AZD9291 treatment. If male patients wish to father children they should be advised to arrange for freezing of sperm samples prior to the start of AZD9291 treatment.

3. If medically feasible, patients taking regular medication, with the exception of potent inhibitors or inducers of CYP3A4 (see above), should be maintained on it throughout the access program period (30 days post-last dose). Patients taking concomitant medications whose disposition is dependent upon CYP3A4 and breast cancer resistance protein (BCRP) and which have a narrow therapeutic index should be closely monitored for signs of changed tolerability as a result of increased exposure of the concomitant medication whilst receiving AZD9291. Patients taking concomitant medications whose disposition is dependent upon CYP3A4, CYP1A2, CYP2C or p-

glycoprotein and which have a narrow therapeutic index should be closely monitored for reduction in therapeutic activity as a result of the reduced exposure of the concomitant medication while receiving AZD9291. Guidance on medications to avoid, medications that require close monitoring and on washout periods is provided (see Appendix A).

Up to 1.5-fold increase in exposure may occur in statin exposure when coadministered with AZD9291. It is recommended that the starting and maintenance dose of statins should be as low as possible and should be guided by the statin prescribing information.

Patients taking warfarin should be monitored regularly for changes in prothrombin time or international normalized ratio (INR).

4. Patients who wear contact lenses must discontinue wearing their lenses if they have any mild to moderate eye symptoms (CTCAE grade ≤ 2) while receiving treatment with AZD9291 until at least one week after symptoms have resolved. If a patient has a recurrence of eye symptoms or experiences any severe (CTCAE grade ≥ 3) ocular events, they must discontinue wearing their contact lenses until at least one week after treatment with AZD9291 is permanently discontinued. Patients must not use any eye drops or ointment for treatment of eye symptoms, unless agreed to by a access program doctor, at any time during the access program until 1 week after AZD9291 has been permanently discontinued. Patients should consult their clinician promptly if they have any concerns.

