4.3 Follow-up period

Descriptions of the procedures for this period are included in the Study Plan (Table 1) with exceptions of the following specific requirements for the follow-up period: Patients will return to the clinic/hospital for follow-up assessments 30 days (± 7 days) after their last dose. If a patient discontinues AZD9291, they will also attend a study treatment discontinuation visit.

5. Study assessments

The investigator will ensure that data are recorded on the electronic Case Report Forms (eCRFs) as specified in the study protocol and in accordance with the instructions provided.

The investigator ensures the accuracy, completeness, and timeliness of the data recorded and of the provision of answers to data queries according to the sponsor agreement. The investigator will sign the completed eCRFs. A copy of the completed eCRFs will be archived at the study site.

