6.6.2 Paternal exposure

Pregnancy of the subject's partners is not considered to be an adverse event. However, the outcome of all pregnancies (spontaneous miscarriage, elective termination, ectopic pregnancy, normal birth or congenital abnormality) should if possible be followed up and documented. To capture information about a pregnancy from the partner of a male subject, the male subject's partner consent must be obtained to collect information related to the pregnancy and outcome; the male subject should not be asked to provide this information. A consent form specific to this situation must be used. The outcome of any conception occurring from the date of the first dose until 6 months after dosing ends should be followed up and documented.

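### The only contraceptive measure stated for male patients can end before the period in which the protocol says they should not father a child, and the start of its 3-month washout is not defined

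*Combined protocol and SAP*

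**What the plan says.** Section 3.8 opens by applying its restrictions "while the patient is receiving AZD9291 and for the specified times before and after". Item 2, on male patients, then gives three instructions:

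- Condom use applies to every female partner, and its period is given as "during the trial and for a washout period of 3 months".
- On fathering a child, the text reads: "Patients should not father a child for 6 months after completion of AZD9291 treatment".
- Sperm donation is barred over the time on treatment and the 6 months that follow it.

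Section 6.6.2 (Paternal exposure) has sites track and record what becomes of a "conception occurring from the date of the first dose until 6 months after dosing ends".

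Two other places touch the subject without adding a duration. Inclusion criterion 8 in Section 3.1 says "Male patients should be willing to use barrier contraception" and refers the reader to Restrictions. Exclusion criterion 13 in Section 3.2 deals with birth control as a condition of entry.

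**The concern.** Three statements about male reproductive risk run to 6 months after treatment. The one practical measure that would prevent a conception runs for 3 months, from a point the text does not fix. A man who follows item 2 to the letter may have no stated means of contraception for part of the time in which he is told not to father a child. The protocol gives no reason for the difference.

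What is at stake is the clarity of a safety instruction. It protects partners and any pregnancy, and partners are not themselves trial participants. With about 10 sites planned, investigators could also advise men differently, depending on when each takes the washout to begin.

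**Working it through.** No sample size, error rate or event count enters this point. The check compares stated durations.

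**Inputs**

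| Period | Length | Counted from | Source |
|---|---|---|---|
| Condom use | trial plus 3 months | not stated | 3.8, item 2 |
| Not fathering a child | 6 months | completion of AZD9291 | 3.8, item 2 |
| Not donating sperm | 6 months | discontinuation of AZD9291 | 3.8, item 2 |
| Follow-up of conceptions | 6 months | end of dosing | 6.6.2 |
| Follow-up visit | 30 days (± 7 days) | last dose | 4.3 |

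The three 6-month periods all start at the end of treatment, so they agree with one another. Only the condom period differs, both in length and in the lack of a named starting event. By contrast, item 1 of the same section counts the contraception period for women explicitly from discontinuation of AZD9291.

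**Formula.** Let t be the time in months from the last dose to the start of the washout. Condom use then ends at t + 3 months after the last dose, and the uncovered interval is

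gap = max(0, 6 − (t + 3)) = max(0, 3 − t).

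**Reading A: washout counted from the last dose (t = 0).** Gap = 6 − 3 = 3 months, that is, months 4 to 6. The opening line of Section 3.8 and the word washout both point this way.

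**Reading B: washout counted from the follow-up visit.** Section 4.3 places "follow-up assessments 30 days (± 7 days) after their last dose". Taking 30 days as one month, t = 1 and gap = 3 − 1 = 2 months. The visit window runs from 23 to 37 days:

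- 23/30 = 0.77 months, so gap = 3 − 0.77 = 2.23 months.
- 37/30 = 1.23 months, so gap = 3 − 1.23 = 1.77 months.

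**Reading C: washout counted from a later end of trial participation.** The note to Figure 1 in Section 1.4 keeps patients who stop for reasons other than progression on scheduled tumour assessments until progression. For such a man t may exceed 1 month. The gap shrinks accordingly and is zero once t reaches 3 months.

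**Does another section close the gap?** Criterion 8 in Section 3.1 has no duration of its own and points back to Section 3.8. Criterion 13 in Section 3.2 governs entry, not the period after treatment. Section 6.6.2 sets a documentation window and asks for no contraceptive measure. None of them supplies one for the later part of the 6 months.

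**The case against.** The strongest reply is that the instructions do not conflict. One sets a method and the other an outcome, and a man can comply with both. The condom rule covers all female partners without regard to whether they can conceive, and its 3 months equals the period given for women in item 1. It may therefore serve a different purpose from the 6-month rule. The documents give no rationale for either period, so it cannot be shown that all of them address one and the same risk, nor that they must be equal. This part of the reply stands. It limits the point to a missing measure and an undefined start. It does not remove the point, because the text neither explains the difference nor says how conception is to be avoided once condom use ends.

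A reader might infer three stronger things that the documents do not support:

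- **That the protocol tells men to stop contraception while still at risk.** No sentence does so, and the instruction not to father a child continues to 6 months.
- **That every male patient has a 3-month gap.** That holds only if the washout starts at the last dose, which the text favours but does not state.
- **That the condom period decides which partner pregnancies are followed up.** Section 6.6.2 fixes that window itself, from first dose to 6 months after dosing ends, whatever the condom period.

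**Conclusion.** The mismatch is real and minor. The stated contraceptive measure for men can end before the period in which conception is to be avoided. The shortfall is at most 3 months. It is about 2 months (1.8 to 2.2 across the visit window) if the washout runs from the 30-day visit, and shorter or nil with longer participation. The upper figure assumes that the washout starts at the last dose.

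The conclusion is confined to the wording of a participant-safety rule. It has no bearing on the response endpoint, the two-stage design, the error rates or the analyses. It does not imply that any of the stated durations is wrong. Consent pages are not in the public copy, so whether the consent form already deals with this cannot be checked.

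**What to change.** The sponsor should make two changes to Section 3.8, item 2:

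1. Reconcile the condom period with the no-fathering and sperm-donation periods in the same item and with the conception follow-up period in Section 6.6.2. If the difference is intended, state the reason and say how conception is to be avoided after condom use ends.
2. Name the event from which the washout is counted.

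The reference to Restrictions in criterion 8 of Section 3.1 should then be checked against the revised text, and the consent form made consistent with it. The choice of duration belongs to the sponsor.

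The cost is a sentence or two in the protocol and, if needed, one in the consent form, with the ethics committee approval that Section 10.5 requires where they apply. No data collection or analysis changes.
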